# **ABBREVIATIONS:**

AE Adverse Event

ALT Alanine Aminotransferase
ALC Absolute Lymphocyte Count
APC Antigen Presenting Cells
AST Aspartate Aminotransferase

BUN Blood Urea Nitrogen
BTC Biliary Tract Cancer
CBC Complete Blood Count

CMP Comprehensive Metabolic Panel

CR Complete Response
CT Computed Tomography

CTCAE Common Terminology Criteria for Adverse Events

CTSU Clinical Trials Support Unit
DDR DNA Damage Response
DILI Drug-Induced Liver Injury
DLT Dose Limiting Toxicity

DSMC Data and Safety Monitoring Committee

H&P History & Physical Exam

HRPP Human Research Protections Program

IDH Isocitrate dehydrogenaseIHC ImmunohistochemistryIND Investigational New DrugIRB Institutional Review Board

IV (or iv) Intravenously

MTD Maximum Tolerated Dose
NCI National Cancer Institute
ORR Overall Response Rate

OS Overall Survival

PBMCs Peripheral Blood Mononuclear Cells

PD Progressive Disease
PFS Progression Free Survival
PI Principal Investigator
p.o. per os/by mouth/orally
PR Partial Response

PRC Protocol Review Committee SAE Serious Adverse Event

SD Stable Disease

TIL Tumor Infiltrating Leukocytes

UaP Unanticipated Problem WBC White Blood Cells

# **STUDY SCHEMA**

1° endpoint - PFS rate 4 months 2° endpoints – ORR, median PFS & OS

# **STUDY SYNOPSIS**

| Title                 | Phase II Multi-center Study of PARP inhibitor Rucaparib in Combination with Anti-PD-1 Antibody Nivolumab in Patients with Advanced or Metastatic Biliary Tract Cancer Following Platinum Therapy.                                                                                                                                                                                                                                                                                                                                                                                                                                                                                                                                                                                                                                                                                                                |  |  |  |  |  |
|-----------------------|------------------------------------------------------------------------------------------------------------------------------------------------------------------------------------------------------------------------------------------------------------------------------------------------------------------------------------------------------------------------------------------------------------------------------------------------------------------------------------------------------------------------------------------------------------------------------------------------------------------------------------------------------------------------------------------------------------------------------------------------------------------------------------------------------------------------------------------------------------------------------------------------------------------|--|--|--|--|--|
| Phase                 | Phase II                                                                                                                                                                                                                                                                                                                                                                                                                                                                                                                                                                                                                                                                                                                                                                                                                                                                                                         |  |  |  |  |  |
| Methodology           | Single arm, open-label                                                                                                                                                                                                                                                                                                                                                                                                                                                                                                                                                                                                                                                                                                                                                                                                                                                                                           |  |  |  |  |  |
| Study Duration        | 3 years                                                                                                                                                                                                                                                                                                                                                                                                                                                                                                                                                                                                                                                                                                                                                                                                                                                                                                          |  |  |  |  |  |
| Study Center(s)       | Multi-Center: 3 sites total including lead site: University of Michigan                                                                                                                                                                                                                                                                                                                                                                                                                                                                                                                                                                                                                                                                                                                                                                                                                                          |  |  |  |  |  |
| Objectives            | 
 
Primary objective:         
 
Determine the PFS rate at 4 months in patients with advanced BTC treated with rucaparib and nivolumab following 1st line platinum based therapy.
 
 
 
Secondary objectives:         
 
Evaluate the ORR and median PFS and OS as measured from start of study treatment and start of initial platinum therapy in patients with advanced BTC.
 
Evaluate the safety of rucaparib and nivolumab in this patient population.
 
Evaluate the ORR, median PFS and OS in patients with and without DNA damage response (DDR) and isocitrate dehydrogenase (IDH) signatures.
 
 
 
Exploratory objectives:         
 
To explore biomarkers of response and mechanisms of resistance based on the exploratory analysis of tumor tissue obtained through serial biopsies and blood.

 |  |  |  |  |  |
| Number of
Subjects | 32 patients meeting intent-to-treatment guidelines. Up to 35 patients may be enrolled to allow for a small number of patients to be replaced, if necessary.                                                                                                                                                                                                                                                                                                                                                                                                                                                                                                                                                                                                                                                                                                                                                      |  |  |  |  |  |
| Eligibility Criteria  | 
 
Patients must have a pathologically confirmed adenocarcinoma of the biliary tract (intra-hepatic, extra-hepatic (hilar, distal) or gall bladder) that is not eligible for curative resection, transplantation, or ablative therapies. Tumors of mixed histology are excluded.
 
Patients must have received 1st line platinum-based chemotherapy for advanced BTC for 4-6 months (16-24 weeks) without radiologic or clinical progression. Last systemic infusion of 1st line platinum-based therapy may not be more than 4 weeks from study informed consent. Prior peri-operative chemotherapy is permitted provided it was completed > 6 months from start
 
                                                                                                                                                                                                |  |  |  |  |  |

- of platinum-based therapy for advanced disease.
- 3. Prior surgical resection, radiation, chemoembolization, radioembolization or other local ablative therapies are permitted if completed ≥ 4 weeks prior to enrollment AND if patient has recovered to ≤ grade 1 toxicity.
- 4. Patients must have radiographically measurable disease (as per RECISTv1.1) in at least one site not previously treated with radiation or liver directed therapy (including bland, chemo- or radio-embolization, or ablation) either within the liver or in a metastatic site unless the patient has had complete response to 1st line platinum-based therapy.
- 5. Age ≥18 years
- 6. Child-Pugh score of A or B7
- 7. ECOG performance status of 0-1
- 8. Ability to understand and willingness to sign IRB-approved informed consent
- 9. Available archived tissue (FFPE block or 20 unstained slides from prior core biopsy or surgery).
- 10. Must be able to tolerate CT and/or MRI with contrast
- 11. Adequate organ function obtained ≤2 weeks prior to registration (absolute neutrophil count ≥1500/mm³, hemoglobin ≥9 g/dL, platelets ≥100,000/mm³, serum creatinine ≤ 1.5 x upper limit normal (ULN), creatinine clearance >= 50 mL/min, albumin ≥3.0 g/dL, AST/ALT ≤3.0 x ULN (≤5 x ULN if liver metastasis), total bilirubin ≤ 1.5 x upper limit normal.
- 12. Must not have a diagnosis of immunodeficiency, or received systemic steroid therapy, or any other form of immunosuppressive therapy within 14 days prior to trial treatment. Short bursts of steroids of 5-7 days (for COPD exacerbation or other similar indication) are allowed.
- 13. No prior history of solid organ transplantation or brain metastasis (unless treated and stable).
- 14. Must not have undergone a major surgical procedure < 4 weeks prior to registration.
- 15. Must not have an active second malignancy other than non-melanoma skin cancer or cervical carcinoma in situ. Patients with history of malignancy are eligible provided primary treatment of that cancer was completed > 1 year prior to registration and the patient is free of clinical or radiologic evidence of recurrent or progressive malignancy.
- 16. Must have no ongoing active, uncontrolled infections (afebrile for > 48 hours off antibiotics).
- 17. Must not have received a live vaccine within 30 days of planned start of the study therapy.
- 18. Must not have a psychiatric illness, other significant medical illness, or social situation which, in the investigator's opinion, would limit compliance or ability to comply with study requirements.
- 19. Women must not be pregnant or breastfeeding since rucaparib and/or nivolumab may harm the fetus or child. All females of childbearing potential (not surgically sterilized and between menarche and 1-year post menopause) must have a blood or urine test to rule out pregnancy within 2 weeks prior to registration.
- 20. Women of child-bearing potential and men must agree to use 2 methods of adequate contraception (hormonal plus barrier or 2 barrier forms) OR abstinence prior to study entry, for the duration of study participation, and for 6 months (for women) and 7 months (for men) following completion of study therapy.
- 21. Participants must not have an active, known or suspected autoimmune disease which may affect vital organ function, or has/may require systemic immunosuppressive therapy for management. Participants with type I diabetes mellitus, hypothyroidism only requiring hormone replacement, skin disorders (such as vitiligo, psoriasis, or alopecia) not requiring systemic

|                                              | treatment, or conditions not expected to recur in the absence of an external trigger are permitted to enroll.  22. Participants must not have a condition requiring systemic treatment with either corticosteroids (>10 mg daily prednisone equivalent) or other immunosuppressive medications within 14 days of start of treatment. Inhaled or topical steroids, and adrenal replacement steroid doses >10 mg daily prednisone equivalent, are permitted in the absence of active autoimmune disease.                                                                                                                                                                                                                                                                                                                                                                                                                                                                                                                                                                                                                                                                                                                                                                                                                                                                                                                                                                                                                                                                                                                                                                                                                                                                                                                                                                             |
|----------------------------------------------|------------------------------------------------------------------------------------------------------------------------------------------------------------------------------------------------------------------------------------------------------------------------------------------------------------------------------------------------------------------------------------------------------------------------------------------------------------------------------------------------------------------------------------------------------------------------------------------------------------------------------------------------------------------------------------------------------------------------------------------------------------------------------------------------------------------------------------------------------------------------------------------------------------------------------------------------------------------------------------------------------------------------------------------------------------------------------------------------------------------------------------------------------------------------------------------------------------------------------------------------------------------------------------------------------------------------------------------------------------------------------------------------------------------------------------------------------------------------------------------------------------------------------------------------------------------------------------------------------------------------------------------------------------------------------------------------------------------------------------------------------------------------------------------------------------------------------------------------------------------------------------|
|                                              | 23. Patients may not have previously received anti PD1/PDL1 antibodies or PARP inhibitor for treatment of this cancer.                                                                                                                                                                                                                                                                                                                                                                                                                                                                                                                                                                                                                                                                                                                                                                                                                                                                                                                                                                                                                                                                                                                                                                                                                                                                                                                                                                                                                                                                                                                                                                                                                                                                                                                                                             |
| Study Product(s),
Dose, Route,
Regimen | Rucaparib 600 mg PO BID days 1-28
Nivolumab 240 mg IV days 1 and 15                                                                                                                                                                                                                                                                                                                                                                                                                                                                                                                                                                                                                                                                                                                                                                                                                                                                                                                                                                                                                                                                                                                                                                                                                                                                                                                                                                                                                                                                                                                                                                                                                                                                                                                                                                                                             |
| Duration of Administration                   | Patients may continue treatment for 2 years in absence of disease progression or unacceptable toxicity.                                                                                                                                                                                                                                                                                                                                                                                                                                                                                                                                                                                                                                                                                                                                                                                                                                                                                                                                                                                                                                                                                                                                                                                                                                                                                                                                                                                                                                                                                                                                                                                                                                                                                                                                                                            |
| Statistical
Methodology                   | The investigators intend to enroll patients with stable or responding advanced disease after at least 4 months of 1st line platinum therapy, and expect a large majority of those patients to have previously received between 4 to 6 months of platinum therapy. The sample size of this trial is based on the hypothesis that the expected proportion of patients surviving without progression after 4 months of study treatment will be improved with investigational therapy. We will accrue 32 evaluable patients to this trial. Evaluable patients are compliant with study treatment and observed for progression-free survival events, progression, death, or lack of events following up to 4 months of study treatment. Patients noncomplaint with treatment or lost to follow-up will be replaced. Based on the ABC-02 trial, PFS was estimated to be 72% and 60% at 4 and 6 months after first line gemcitabine and cisplatin, similar to the initiation point of our study and PFS was 51% and 32% at 8 and 10 months, similar to the end of the treatment period for the primary outcome assessment in this trial. Using a conditional probability argument, combined with the assumption that patient accrual to this study will follow an approximate uniform distribution over the 4 to 6 months of primary therapy for the patients accrued, we can accept the average of the PFS estimates for each period (4-6 months (66%) and 8-10 months (41.5%)) to correspond to our trial time period. We can then standardize the ABC-02 PFS data so that the 4-6 month estimate is 100% and the estimate for 4 months thereafter is 63%. For our trial, we hope to improve the PFS rate from 63% for these patients to 85%. With our proposed sample size of 32 patients this trial will have 80% power to detect this difference significantly using a 1-sided test. |

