# 6.0 STUDY PROCEDURES

#### 6.1 Screening/Baseline Procedures

Assessments performed exclusively to determine eligibility for this study will be done only after obtaining informed consent. Assessments performed for clinical indications (not exclusively to determine study eligibility) may be used for baseline values even if the studies were done before informed consent was obtained.

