| Other labs                        |                        | Х       |       |         | Х     |                            |                        |                          |
| CA 19-9 (or CEA)                  | X                      | Х       |       |         | Х     |                            | Х                      |                          |
| PT, PTT                                       | X                      |         |       |         |       |                            |                        |                          |
| Pregnancy Test⁵                               | X                      | Χ       |       |         | Х     |                            |                        |                          |
| Concomitant
Medication Review              | Х                      | Х       |       |         | Х     |                            |                        |                          |
| Scans with Tumor
Measurements  | Х                      |         |       |         | Х     |                            |                        |                          |
| Research Blood                    |                        | Χ       |       |         | Χ     |                            | Х                      |                          |
| Tissue                            | Х                      |         |       |         | Х     |                            | Х                      |                          |
| Study Drug
Administration      |                        | Х       |       | Х       | Х     | Х                          |                        |                          |
| Survival Follow-up                            |                        |         |       |         |       |                            |                        | Х                        |

1. All screening procedures to be completed within 2 weeks of registration, except imaging and informed consent which should be ≤ 4 weeks. Protocol treatment is to begin ≤14 calendar days of registration.

2. Comprehensive metabolic panel includes BUN/creatinine, sodium, potassium, chloride, glucose, calcium, alkaline phosphatase, AST, ALT, total bilirubin and total protein.

3. Amylase, lipase, random cortisol, TSH, free T4 and T3 on cycle 1 day 1, and then day 1 of every odd numbered cycle.

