#### 7.1.4 Response Criteria

# 7.1.4.1 Evaluation of Target Lesions

Prior to the first PD assessment, patients will be evaluated according the following RECISTv1.1 response:

Complete Response (CR): Disappearance of all target lesions, determined by two separate observations conducted not less than 4 weeks apart. There can be no appearance of new lesions.

Partial Response (PR): At least a 30% decrease in the sum of the longest diameter (LD) of target lesions, taking as reference the baseline sum LD. There can be no appearance of new lesions.

Progressive Disease (PD): At least a 20% increase in the sum of the LD of target lesions (with a minimum absolute increase of 5 mm), taking as reference the smallest sum LD recorded since the treatment started, or the appearance of one or more new lesions.

Stable Disease (SD): Neither sufficient shrinkage to qualify for PR (taking as reference the baseline sum LD) nor sufficient increase to qualify for PD (taking as reference the smallest sum LD since the treatment started).

After the first PD assessment per RECISTv1.1 (=irSD per irRECIST), patients will be evaluated for irPD at least 4 weeks apart according to the following definition:

Immune-related Progressive Disease (irPD): At least a 20% increase in the sum of the LD of target lesions (with a minimum absolute increase of 5 mm), taking as reference the smallest sum LD recorded since the treatment started, or appearance of new lesions since the last evaluation.

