#### 11.0 STATISTICAL CONSIDERATIONS

#### 11.1 Study Design/Study Endpoints

This protocol will enroll patients with advanced unresectable BTC who have received at least 4 months of platinum-based front-line systemic chemotherapy with last dose within 4 weeks of informed consent. The primary endpoint is PFS rate at 4 months following the initiation of study treatment. Secondary endpoints include the calculation of the ORR, median PFS and OS (from start of study treatment and 1st line platinum-based therapy), and the incidence of adverse events.

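### Nothing requires the baseline tumour scan to follow the last platinum infusion, so platinum shrinkage can be credited to study treatment, mainly in the ORR

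*Combined protocol and SAP*

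**What the plan says.** **Platinum timing.** Synopsis criterion 2 and section 3.1.2 say the last infusion of first-"line platinum-based therapy may not be more than 4 weeks from study informed consent". Section 11.1 repeats the rule: "front-line systemic chemotherapy with last dose within 4 weeks of informed consent". Both set a maximum gap to consent, with no minimum gap and no link to imaging. Criterion 3 is different: it sets a minimum gap for prior local treatment, where "other local ablative therapies are permitted if completed ≥ 4 weeks prior to enrollment".

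**Scan timing.** Footnote 1 of the study calendar (section 6.2) reads: "All screening procedures to be completed within 2 weeks of registration, except imaging and informed consent which should be ≤ 4 weeks". It adds: "Protocol treatment is to begin ≤14 calendar days of registration". Section 7.1.3 caps baseline evaluations at 4 weeks before treatment and asks that they be done as near to treatment start as possible. Section 6.1 provides that assessments made for clinical reasons "may be used for baseline values even if the studies were done before informed consent was obtained".

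**Use of the baseline.** In section 7.1.4.1, PR is a fall of at least 30%, "taking as reference the baseline sum LD. There can be no appearance of new lesions". PD is a rise of at least 20% and 5 mm over the smallest sum recorded since treatment started. At the first on-study scan (8 ± 1 weeks) no earlier on-study sum exists, so the baseline has to be the reference.

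**The concern.** Entry requires 4 to 6 months of platinum without progression, so restaging scans made during platinum are likely to exist, and section 6.1 admits them. If such a scan becomes the baseline and another infusion follows, the reference sum predates part of the first-line treatment. Any further shrinkage from that infusion is then read as an effect of rucaparib plus nivolumab. The size at first study dose is never recorded, so growth from that size is understated until a smaller sum is recorded on study. The trial has one arm, so no control group shares the error. ORR is a secondary endpoint and the 4-month PFS rate is the primary one.

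**Working it through.** **1. Is the order permitted?** Take this sequence, with no day 0:

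| Day | Event | Rule met |
|---|---|---|
| −28 | Clinical restaging CT, used as baseline | 6.1; 28 days before day 1 (7.1.3) |
| −27 | Last platinum infusion | 2 days before consent (limit 4 weeks) |
| −25 | Consent | 11 days before registration (limit 4 weeks) |
| −14 | Registration | scan 14 days earlier (limit 4 weeks) |
| 1 | First study dose | 14 days after registration (limit 14 days) |

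It meets every hard limit. Footnote 1 read alone would allow 28 + 14 = 42 days from scan to dose, against 28 in section 7.1.3.

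**2. The plan's own figure.** Section 11.2: 0.415/0.66 = 0.629, used as 63%; alternative 85%; n = 32; one-sided 5%. By exact binomial, the smallest count with one-sided error at or below 5% is 26/32: P(X ≥ 26) = 0.0215 at 63% and 0.805 at 85%. The stated 80% power reproduces. At 25/32 the error is 0.0523.

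**3. Thresholds.** Let s be the fraction by which the target sum shrinks between the baseline scan and the first dose (assumed).

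- On-study shrinkage needed for PR: 1 − 0.7/(1 − s)
- On-study growth needed for PD while baseline is the reference: 1.2/(1 − s) − 1

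| s | PR needs | PD needs |
|---|---|---|
| 0 | 30% | 20% |
| 5% | 26.3% | 26.3% |
| 10% | 22.2% | 33.3% |
| 15% | 17.6% | 41.2% |

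For example, 100 mm at baseline, 85 at first dose and 70 on study scores −30% (PR), but the on-study change is 70/85 − 1 = −17.6%. One such PR adds 1/32 = 3.1 points to the ORR.

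**4. How much reaches the 4-month PFS rate?** Assume constant growth g per 8 weeks from first dose, with scans at weeks 8 and 16.

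- True PD by week 8 means g ≥ 20%. The week-16 sum is then at least 20% above the week-8 sum. If the baseline is smaller than the week-8 sum, the rise over baseline is larger still. PD is scored at week 16 for any s. For example, 100, 90, 115 mm scores +15% at week 8 although true growth is 27.8%; at the same rate week 16 is 115 × 1.278 = 146.9, or +46.9% over baseline.
- True PD first reached by week 16 needs (1 + g)² ≥ 1.2, so g ≥ 9.5%. It is missed when g < 20% and (1 − s)(1 + g)² < 1.2, that is g < √(1.2/(1 − s)) − 1.

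| s | Growth per 8 weeks that is missed at week 16 |
|---|---|
| 5% | 9.5% to 12.4% |
| 10% | 9.5% to 15.5% |
| 15% | 9.5% to 18.8% |

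For example, s = 10% and g = 12%: 100, 90, 100.8, 112.9 mm. Scored +12.9% (SD); true +25.4%.

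**5. Effect on the test.** If missed PD lifted the apparent null rate above 63% (lift assumed), P(X ≥ 26) would be 0.046 at 66% and 0.074 at 68%. A lift to 66% is about one patient in 32.

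**6. Opposite direction.** If the sum instead regrows by 10% before day 1, PD needs only 1.2/1.1 − 1 = 9.1% growth and PR needs 1 − 0.7/1.1 = 36.4% shrinkage.

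**The case against.** A reader might infer that the gap biases the primary result in favour of the regimen as a matter of course. The documents do not support that, for these reasons:

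- Step 4 confines the effect on 4-month PFS to a band of slower growth. New lesions, non-target progression, clinical progression and death do not depend on the baseline sum.
- The direction is not fixed. The example sequence leaves nearly four platinum-free weeks before day 1, and regrowth in that time works against the regimen.
- Moving from 25/32 to 26/32 shows that any single reclassification near the cut-off matters. It does not show that this gap causes one.
- Neither the 5% to 15% shrinkage nor the share of patients affected can be taken from the documents. The shrinkage would have to come late, after months of platinum.

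Section 7.1.3 also asks for evaluations near treatment start, and the sequence in step 1 sits at the outer limits. That instruction discourages the sequence, but it neither prohibits it nor sets the order. Table 5 asks for confirmation of PR at least 4 weeks later, which removes short-lived shrinkage; but confirmation uses the same baseline sum, so it does not correct the reference.

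Lastly, a scan the day after an infusion would satisfy an order rule and still miss most of that dose's effect. This stands: an order rule removes platinum given after baseline, not all carry-over.

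**Conclusion.** The gap is real. The rules allow a baseline scan that predates the last platinum infusion, and any resulting shrinkage is credited to study treatment. The main effect is on ORR: the PR threshold falls from 30% to between 26% and 18% for an assumed further shrinkage of 5% to 15%, in affected patients with measurable disease.

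Progression in target lesions can be called late at the first on-study scan. For the 4-month PFS rate the effect is limited to target-lesion growth of about 10% to 12%, 15% or 19% per 8 weeks, for shrinkage of 5%, 10% or 15%. That result assumes constant growth and a second scan before 4 months. Growth that slows after week 8, or a second scan late in its window, would leave somewhat more progression unscored. Whether a first, unconfirmed PD under the combined RECIST/irRECIST scheme counts at 4 months is a separate question.

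The number of affected patients is unknown and the direction is not certain. The sample size and stated power are not in dispute.

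**What to change.** State in Synopsis criterion 2, section 3.1.2 and calendar footnote 1 that the baseline tumour scan must be obtained after the last first-line platinum infusion and as near as practicable to the first study dose, within the section 7.1.3 limit of 4 weeks before treatment. Reconcile footnote 1, which ties imaging to registration, with that limit.

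Record the dates of the baseline scan and the last infusion for every patient, including those already enrolled. Report ORR and 4-month PFS with and without patients whose scan preceded the last infusion. Note beside that analysis that it addresses platinum given after baseline and not all carry-over from a dose given shortly before it.

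The cost is small: one sentence in each of the three places, two dates per patient and one sensitivity analysis. The scan is already required. Some existing clinical scans could no longer serve as baseline, so in those patients the screening scan would be done later or repeated.
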